4.4.4 PTEN

PTEN, like BRAF, is another component of the MAPK signaling pathway and therefore its mutational status could affect the efficacy of cetuximab. In the Laurent-Puig study discussed above (JCO 2009) they also evaluate this marker. PTEN expression was absent in 19.9% of KRAS WT patients and was associated with both progression-free survival and overall survival. Similarly, another study (Loupakis et al. JCO 2009) evaluated the predictive role of loss of PTEN expression in metastases in patients with colorectal cancer in progression to irinotecan treated with irinotecan plus cetuximab. In this study, the loss of PTEN expression in metastases was shown to be associated with worse progression-free survival ($p = 0.005$).

For all this, we consider that the expression of PTEN, together with BRAF, is another of the markers that we must include in the characterization of the MAPK pathway in this protocol.

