4.5 Rationale for this trial

Advanced and / or metastatic colorectal cancer (CCRA) is a heterogeneous disease and the classification of patients is currently poor. Approximately twenty percent of patients have favorable stages (less than 4 nodules in the liver and less than 5 cm) and are suitable for local treatments (surgery or local ablative therapies). Additionally, 10-15% of patients have a poor functional status (ECOG > 2) or are impaired due to geriatric syndromes and / or co-morbidity with diseases that oppose any strategy other than the best supportive therapy. . The rest of the patients (suitable patients not suitable for radical surgery) constitute the population of patients treated with palliative therapies. Despite this, not all patients have the same prognosis. Patients with ECOG 0.1 and LDH levels <ULN (intermediate-risk patients) have better PFS and OS regardless of therapy in all randomized clinical trials (de Gramont et al, JCO 2000; Douillard et al, Lancet 2000; Koopman et al, 2007).

The CRYSTAL study shows a benefit in PFS (1.5 months) in non-mutated KRAS from FOLFIRI plus cetuximab compared to FOLFIRI alone. Currently, the selection of patients for treatment with cetuximab is based on the KRAS mutational status, which allows selecting those patients who will not respond to therapy. Other activity markers should be evaluated.

PTEN

The cytoplasmic expression of PTEN is inversely associated with PFS in colorectal cancer. There are two main retrospective studies evaluating PTEN expression in patients treated with cetuximab. Prospective validation of this marker has not yet been developed.

Clinical Hypothesis

Our hypothesis is that the proposed markers will make it possible to select those patients who will benefit the most from biweekly cetuximab treatment.

Single-arm, multicenter, prospective phase II clinical trial for biomarker validation in patients with advanced and / or metastatic colorectal cancer with non-mutated KRAS gene treated with chemotherapy plus biweekly cetuximab as first-line therapy

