Tumour sample quality from primary or metastatic tissues was checked, and blood samples were collected at baseline and every 3 months along with abdominopelvic CT scan imaging. The feasibility of bi-weekly cetuximab in combination with chemotherapy (FOLFOX or FOLFIRI) was evaluated by means of progression free survival (PFS), overall survival (OS), objective response rate (ORR), and reported toxicities. The trial hypothesis was that the proposed biomarkers would allow identifying those patients who would benefit the most from bi-weekly cetuximab therapy. KRAS and NRAS mutations were evaluated by pyrosequencing, BRAF and PI3K mutations by RT-qPCR, and PTEN expression by immunohistochemistry. The PFS (time from the signature of the ICF date to PD or death) and OS (time from the signature of the ICF date to death) were analysed and compared between patients with: wild-type (wt) BRAF (wt-BRAF) vs mutant BRAF, and in patients with increased PI3K pathway activation (PI3K mutant or loss of PTEN expression) vs low PI3K pathway activation (wtPI3K and preserved PTEN expression).

Sponsor: Grupo Español Multidisciplinar en Cáncer Digestivo (GEMCAD) Spanish Multidisciplinary Group in Digestive Cancer

Protocol number: GEMCAD 1002 - POSIBA

Clinical Phase: II

Study dates: Study initiation date: first patient enrolled on 27/JUN/2011
Study completion date (last patient completed): 20/JUN/2017

[figure not shown]
This study, including the archiving of essential documents, was performed in compliance with ICH Good Clinical Practice (GCP)

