1. SYNOPSIS

NAME OF SPONSOR: GEMCAD

NAME OF FINISHED PRODUCT N/A

NAME OF ACTIVE INGREDIENT(S): CETUXIMAB

Title of Study	A prospective, multicentre, single-arm, phase II clinical trial to evaluate biomarkers in advanced and/or metastatic colorectal cancer patients with wild-type KRAS/NRAS status treated with chemotherapy plus bi-weekly cetuximab as first-line therapy.
Investigator(s)	

Study centre(s)	
-----------------	---

Objectives	
Primary Objective
 
To evaluate BRAF, IGF-1RP/MMP-7 (Double-positive Phenotype/DP), and PI3K-PTEN as well as other relevant biomarkers which may arise during study implementation, to predict PFS in advanced and/or metastatic colorectal cancer patients with wt-RAS tumours treated with standard chemotherapy plus bi-weekly cetuximab as first-line therapy.
 
Secondary Objectives
 
 • To analyse secondary biomarkers (MMP-7, IGF-1, IGFBP-3, amphiregulin, and epiregulin, as well as other relevant biomarkers, which may arise during the study) in the serum and tumour tissues to predict acquired chemoresistance. • OS based on the proposed classification • ORR according to RECIST 1.1 (46) • Safety of treatment with bi-weekly cetuximab at 500 mg/m²
------------	--

Methodology	We conducted a biomarker-evaluation phase II trial. A total of 181 wt KRAS exon 2 patients were evaluated for whole KRAS and NRAS mutations by pyrosequencing, BRAF and PI3K mutations by RT-qPCR, and PTEN expression by immunohistochemistry. Patients were followed every 3 months with abdominopelvic CT-scan imaging and clinical examination. PFS (time from the signature of the ICF date to progression or death) and OS (time from the signature of the ICF date to death) in patients with wt-BRAF vs mutant BRAF and in patients with increased PI3K pathway activation (PI3K mutant or loss of PTEN expression) vs low PI3K pathway activation (wt-PI3K and preserved PTEN expression) were evaluated. Univariate and multivariable analyses of BRAF and PI3K-PTEN together with well-known clinical variables were performed. Safety was evaluated based on type, frequency, and intensity of adverse events related to the combination treatment.
Number of patients	Target events for primary endpoint: Planned: 170 patients Enrolled: Analysed for safety: Analysed for efficacy:

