6.5 STATISTICAL METHODS PLANNED IN THE PROTOCOL & DETERMINATION OF SAMPLE SIZE

6.5.1 STATISTICAL AND ANALYTICAL PLANS

6.5.1.1. Primary endpoint

To quantify if the biomarkers BRAF, IGF-1RP/MMP-7 (DP), DP and PIK3CA-PTEN improve the prediction of 12-months progression-free survival (PFS) over the use of just clinical variables in the study population we compared the area under the curve (AUC) of a ROC curve using scores composed by clinical variables with the AUC of scores with the clinical variables plus each of the biomarkers.

PFS was defined as the time from the signature of the ICF date to the radiological progression date or death (whatever occurs first). Subjects who had not shown PD and had not died at database closing were censored on the last date of radiological assessment. Subjects who had concluded study treatment before 48 weeks, due to any cause, underwent follow-up every 12 weeks as described in the protocol. Subjects who had undergone metastatic surgery were not censored on the surgery date but were followed up every 12 weeks until progression was documented. Subjects who received other treatment schemas maintaining the same strategy (chemotherapy + monoclonal antibody) without documented PD, were not censored at the time of the change of treatment. Progression to first line for these patients was considered when applicable according RECIST, independently of treatment received. If by any cause, the baseline CT scan was the only imaging evaluation performed (e.g., subject refusal to stay in the study or lost to follow-up), the case was censored on the inclusion date +1 day.

Two groups with a higher and lower likelihood for tumor progression until 12 months were determined based on the designated classification of clinical variables and following proposed biomarker categories :

1. wt-BRAF vs mutant BRAF

2. wtPI3K and PTEN >3 vs mutant PI3K or PTEN ≤3
3. Non-DP vs DP

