2. A score was established for each patient by adding up the regression coefficients of the multivariable Cox model present in these patients. If for example PS>0 was a negative predictor for PFS (i.e. regression coefficient is negative; e.g. -0.5) and left side tumour was a positive prognostic factor (regression coefficient was positive, e.g. 0.6) then for a patient with PS>0 and left sided tumour the two scores were added (-0.5 + 0.6=0.1). If a patients has PS=0 then the score to be added is 0, as it is the case for right sided tumour in the example.
3. Using a logistic regression model for the outcome 12-months PFS, a ROC curve was computed to choose the score cut point that classifies most patients correctly 4. Patients were dichotomized according to that cut point.
5. Steps 2 to 4 were repeated, adding each of the three biomarkers.
6. Definition of the discriminating power of the 4 scores for prognosis of or 12-months PFS according to these results were compared via ROC curves.
7. Determination of the most suitable score for 12-months PFS according to these results.

The four scores included in the first multivariate model using clinical factors where PS>0, chemotherapy with FOLFIRI and cetuximab, left sided and resectable liver metastases were considered (Score 1). The additional scores considered the four clinical factors above plus the status of each biomarkers (Score 2: BRAF mutation; Score 3: PI3K mutant or PTEN ≤ 3) and Score 4: Double-positive Phenotype (DP).

All analyses were performed using SAS V9.3 (SAS Institute, Cary, NC, USA) statistical software.

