7. RESULTS

Table 4 Disposition of patients

Patients enrolled	
Received at least one cycle of study treatment	
Evaluable patients	
End of study (evaluable population)	
Death	
Lost to follow-up	
Censored at database closure	
Study completion (24 months of follow-up after PD)	

Table 5 Protocol deviations

Deviation type	Total
Informed consent form	
Efficacy criteria	
Eligibility criteria	
Incorrect dosing regimen	
Other	
Safety	

Table 6. Baseline characteristics by biomarker

	wtBRAF (n=161)	Mutant BRAF (n=20)	p-value*	wtPI3K and PTEN >3 (n=69)	Mutant PI3K or PTEN ≤3 (n=98)	p value*	Non-DP (n=158)	DP (n=23)	p value*
Female									
Mean age (SD)									
Primary location									
Ascending colon									
Transverse colon									
Descending colon									
Sigmoid colon									
Rectum									
Stage									
I									
II									
III									
IV									
Surgery of the primary tumour									
Performance status									
0									
1									
2									
Number of metastatic organs									
0									
1									
2									
3									
4+									
Liver metastasis									
0									
≤3, ≤5 cm									
>3 or >5 cm									
Node metastases¹									
Lung metastases¹									
Peritoneal metastases¹									

Patients with only resectable liver metastases ²									
Chemotherapy									
FOLFOX+Cetuximab									
FOLFIRI+Cetuximab									
Mean Leucocytes (SD)									
Mean Haemoglobin (SD)									
Mean Platelets (SD)									
Mean ALP (SD)									
LDH >450									
Mean CEA (SD)									

¹

- Fisher's exact test for categorical variables and Wilcoxon rank-sum test for ordinal or continuous data

² Missing in one patient The patient does not have metastasis in any other location, and those in the liver are ≤ 3 in number and ≤ 5 cm in size.

Table 7. MEASUREMENTS OF TREATMENT COMPLIANCE

	Total (n=)
Treatment disposition	
Received at least one injection (safety population)	
Efficacy population	
Received at least 12 cycles of cetuximab	
Received at least 12 cycles of chemotherapy+cetuximab	
Received less than 12 cycles of cetuximab	
Received 3 or less administrations of combination	
FOLFOX+cetuximab	
FOLFIRI+cetuximab	
End of Treatment (EOT)	
Reasons for end of treatment	
PD	
PI decision (24 due to surgery, 2 radiotherapy, 2 complete response, 49 others)	

Patient decision	
Toxicity (related to treatment)	
AE (unrelated to treatment)	
No data of EOT available	

Table 8: Patients excluded from the efficacy or safety analysis

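### PI3K-PTEN status exists for only 167 of the 181 efficacy patients, so Score 3 needs a clinical-only comparator from the same 167; the PTEN cut at 3 needs a stated scale and sensitivity analyses

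*SAP*

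**What the plan says.** SAP 6.5.1.1 defines the primary PI3K-PTEN grouping as "wtPI3K and PTEN >3 vs mutant PI3K or PTEN ≤3", and 6.5.1.5 repeats it as "Score 3: PI3K mutant or PTEN ≤ 3". The primary analysis compares the AUC of a clinical-only score (Score 1) with the AUC of clinical variables plus each biomarker (Scores 2 to 4) for 12-month PFS.

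The study description on the SAP title page words the same contrast differently: "increased PI3K pathway activation (PI3K mutant or loss of PTEN expression) vs low PI3K pathway activation (wtPI3K and preserved PTEN expression". The synopsis methodology repeats this. The assay is given only as "PTEN expression by immunohistochemistry". Neither document states the score range, the threshold for loss, or the reason for cutting at 3.

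SAP section 7, Table 6, heads the flagged column "Mutant PI3K or PTEN ≤3 (n=98") and the other PI3K-PTEN column n=69. The BRAF columns are 161 and 20, and the double-positive columns 158 and 23.

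SAP 6.5.1.3 treats missing biomarker data as a significant deviation, and says such patients could not contribute to the primary objective. The synopsis puts 181 patients in the efficacy analysis. Its risk-model paragraph prints one clinical-only AUC, 0.67 (0.60-0.75), and for clinical variables plus PI3K/PTEN 0.69 (0.61-0.76, p = 0.32).

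The prevalence figure behind the marker is in Protocol 4.4.4: "PTEN expression was absent in 19.9% of KRAS WT patients".

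**The concern.** Two things are unclear about one of only three primary biomarkers.

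The first is the set of patients behind the AUC comparison. Fourteen patients counted for efficacy have no PI3K-PTEN status. The SAP does not say whether they are dropped from Score 3, dropped from both scores, or scored as zero for the marker. If they are dropped from Score 3 only, the AUC difference mixes the marker's contribution with a change of patients. The reported difference is small enough for that to matter.

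The second is the definition. A reader cannot tell whether ≤3 is how loss of expression was scored or a wider category. Nor can the date of the cut be established: the SAP carries the date the first patient was enrolled, but it also holds AUC results and a 2017 completion date. Without a scale, a source and separate component counts, a null or positive Score 3 result cannot be related to the PTEN-loss evidence the protocol cites.

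**Working it through.** **Patient counts (SAP Table 6 headers; synopsis efficacy count)**
- BRAF: 161 + 20 = 181. Double-positive: 158 + 23 = 181. Both match the synopsis figure of 181.
- PI3K-PTEN: 69 + 98 = 167. Missing: 181 - 167 = 14, or 14/181 = 7.7%.

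**How far a change of patients could move the clinical AUC**
- Input: clinical-only AUC 0.67, 95% CI 0.60 to 0.75 (synopsis).
- SE = (0.75 - 0.60)/(2 × 1.96) = 0.0383.
- If the CI is from N = 181 and 14 patients are dropped at random to leave n = 167, the AUC difference between subset and full set has variance of about SE² × (N/n - 1) = 0.0383² × 14/167 = 0.000123. The SD is 0.011.
- Reported gain: 0.69 - 0.67 = 0.02. Because both values are rounded to two decimals, the gain lies between 0.01 and 0.03.
- One SD of pure patient change is therefore about half the reported gain (0.011/0.02 = 0.55). If the missing patients differ in prognosis from the rest, the shift could be larger.

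**Size of the flagged group**
- 98/167 = 58.7% of patients with a status (Wilson 95% CI 51% to 66%). Over all 181, the share is 98/181 = 54.1% if none of the 14 is positive and 112/181 = 61.9% if all are.
- This is a composite (mutant PI3K or PTEN ≤3). The cited 19.9% is absent PTEN alone, in another cohort, so the two are not directly comparable.
- PI3K mutation rate needed to reach 58.7% if PTEN loss were 19.9%: with no overlap, 58.7 - 19.9 = 38.8%; under independence, 1 - (1 - 0.587)/(1 - 0.199) = 48.4%.
- Neither document gives a PI3K mutation rate. Assuming 10-20%, PTEN ≤3 alone would be 54.1-48.4% under independence, or 48.7-38.7% with no overlap. That is about 2 to 2.7 times 19.9%.

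The last two steps show that the composite is larger than the cited loss rate readily explains. They do not show why.

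**The case against.** The strongest reply on the patient set is that 6.5.1.3 already excludes patients with missing biomarker data, and that a paired AUC comparison can only use patients who have both scores. The printed p = 0.32 may therefore already rest on the 167. That is possible, and the documents do not show that different sets were compared. But the SAP does not say so. It keeps 181 in the efficacy count and prints a single clinical-only AUC beside all three biomarker scores, two of which have complete status. The reader cannot tell whether 0.67 belongs to 181 or 167 patients.

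On the definition, the reply is that the title page and synopsis state a concept and 6.5.1.1 gives its cut-off. That is a fair reading, and no passage contradicts it. A reader might infer from 59% against 20% that tumours expressing PTEN are counted as loss and the marker is diluted. The documents do not support that. The percentages measure different things. Dilution would also require both that ≤3 is wider than loss and that the added patients lack the effect. Any loss of power worked out on those premises is a worst case for a log-rank test, whereas the primary analysis compares AUCs. The 59:41 split itself costs nothing: by the Schoenfeld formula at 115 events and HR ln(0.30)/ln(0.50) = 1.737, power is Φ(√(115 × 0.587 × 0.413) × ln 1.737 - 1.96) = 83%, the same as at the planned 40:60.

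A reader might also see a reversed marker in the background sentence "The cytoplasmic expression of PTEN is inversely associated with PFS in colorectal cancer". The analysis coding is consistent throughout, with mutant PI3K or low PTEN as the adverse side, so that sentence affects no result.

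**Conclusion.** The point on the patient set holds. Fourteen of 181 patients (7.7%) lack a PI3K-PTEN status, 6.5.1.3 does not fit the synopsis count, and the comparator AUC is not tied to a stated set. The possible shift is about 0.011 (one SD) against a reported gain of 0.02. This assumes that the printed interval comes from 181 patients and that the 14 are missing at random. With p = 0.32 printed for Score 3, what is in doubt is the estimated increment, which could move either way, and not a claimed benefit.

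The definition point holds as an unlinked wording and a missing scale. The 39-48% PI3K mutation rate needed to reconcile 59% with 19.9% is a reason to ask for the components. It is not proof that ≤3 is broader than loss, nor that the cut was chosen after seeing outcomes, since no passage dates the cut. Replacing ≤3 with absent PTEN as the primary grouping is not justified either. The scale is unknown and the AUC under ≤3 is already printed, so a switch now would be made with knowledge of the result.

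**What to change.** **Common patient set.** In SAP 6.5.1.1 and 6.5.1.5, state that Score 3 is compared with Score 1 in the same 167 patients. Refit Score 1 there, compute its AUC there, use a paired AUC test, and print that clinical-only AUC beside Score 3. State how the 14 patients without a status are handled, and reconcile 6.5.1.3 with the synopsis count of 181 and with Table 6.

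**PTEN definition.** Keep ≤3 as the stated grouping. Give the immunohistochemistry scale, the dated source of the cut and its relation to loss of expression, and use one wording on the title page, in the synopsis, in 6.5.1.1 and 6.5.1.5 and in Table 6. Report PI3K-mutant and PTEN ≤3 counts separately. Add absent PTEN (with PI3K mutation) and the ordered PTEN score as sensitivity analyses on the existing data, labelled as such.

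**Cost.** This needs SAP wording and a few further analyses of data already held. Score 1 rests on a slightly smaller set in this one comparison.

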6.5.1.2. Secondary endpoints

- Serum and tumor tissue secondary biomarkers evaluated to predict acquired chemo-resistance including BRAF and PI3K.
- ORR was defined as the incidence of a complete or partial response according to the revised RECIST 1.1 criteria.
- DoR (calculated only for the subjects who present an Overall Response): Time from the first assessment of Overall Response to radiologically-confirmed PD according to the revised RECIST 1.1 criteria. For subjects who showed response and did not show progression, DoR was censored on the last date of assessable disease evaluation reported in the eCRF of the study.
- OS: Time from the signature of the ICF date to date of death. For subjects who did not die or were lost to follow-up on the closing date for data analysis, OS was censored on the date of last contact.
- Safety: Type, frequency, and intensity of AEs related to the combination treatment.

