Title: Prospective, multicenter, single-arm phase II clinical trial for biomarker validation in patients with advanced and / or metastatic colorectal cancer with KRAS gene not mutated treated with chemotherapy plus biweekly cetuximab as first-line therapy.

Study Phase: Phase II

Indication:

Advanced and / or metastatic colorectal cancer (CCRA)

Principal Objective:

Validation of the biomarkers BRAF, IGF1P / MMP7 (DP) and PI3K-PTEN to predict PFS in patients with advanced and / or metastatic colorectal cancer with non-mutated KRAS treated with standard chemotherapy plus biweekly cetuximab as first-line therapy.

Secondary Objectives:

Secondary biological markers (MMP-7, IGF-1 and IGFBP3) will be analyzed in serum and tumor tissue to predict acquired resistance.

OS based on proposed classification

Objective response according to RECIST 1.1 (*E.J. Cancer 2009; 228-47*)

Safety of administration of cetuximab 500 mg / m² every 2 weeks.

Clinical Hypothesis:

Our hypothesis is that the proposed markers will make it possible to select those patients who will benefit the most from biweekly cetuximab treatment.

Study design:

Single-arm prospective phase II clinical trial.

Prior to inclusion in the trial and to confirm eligibility, the investigator or designee will review the status of KRAS, BRAF, IGF1P / MMP7 (DP) and PI3K-PTEN, existing radiological images in addition to any other relevant clinical documents (reports, notes, etc.) to confirm that the subject has previously untreated advanced and / or metastatic colorectal cancer.

FOLFIRI (m) / FOLFOX6 (m) will be administered once every 2 weeks until 6 months of treatment, disease progression (PE), or unacceptable toxicity. Cetuximab will be administered every 2 weeks until disease progression. If patients do not show progression after 6 months of treatment with FOLFIRI (m) and FOLFOX6 (m), they will continue to receive biweekly cetuximab as monotherapy until progression.

Subjects who stop receiving FOLFOX6 (m) / FOLFIRI (m), for example due to toxicity, may receive biweekly cetuximab as monotherapy until disease progression. Following discontinuation of biweekly cetuximab, the treatment period will end and subjects will attend a follow-up safety visit

Single-arm, multicenter, prospective phase II clinical trial for biomarker validation in patients with advanced and / or metastatic colorectal cancer with non-mutated KRAS gene treated with chemotherapy plus biweekly cetuximab as first-line therapy

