4.6.2 Secondary Objectives

Secondary biological markers (MMP-7, IGF-1 and IGFBP3) will be analyzed in serum and tumor tissue to predict acquired resistance.

SG based on proposed classification

Objective response according to RECIST 1.1 (E.J. Cáncer 2009; 228-47)

Describe the safety profile of the Cetuximab 500 mg / m² every 2 weeks administration regimen in the first-line setting including the incidence of AE and significant changes in laboratory parameters.

To assess the objective response rate (ORR) and duration of response (RD) and overall survival (OS) in subjects treated with biweekly cetuximab in combination with FOLFOX6 (m) or FOLFIRI (m) as a first-line chemotherapy regimen. for subjects with metastatic colorectal cancer with non-mutated KRAS, according to the expression of the different proposed biomarkers.

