PTEN, like BRAF, is another component of the MAPK signalling pathway; therefore, its mutational status may affect cetuximab efficacy. In the study by Laurent–Puig et al. (44), this biomarker was also evaluated. PTEN expression was absent in 19.9% of wt-KRAS patients, and was associated with both PFS and OS. Furthermore, another study (45) evaluated the predictive role of PTEN expression loss in mCRC patients treated with irinotecan+cetuximab. This study demonstrated that the loss of PTEN expression was associated with lower PFS ($p=0.005$).

Consequently, we consider that PTEN expression, along with BRAF, is another biomarker that is worth investigating for the characterisation of the MAPK signalling pathway in this protocol.

Other biomarkers

The list of investigated biomarkers was left open to avoid proposals being outdated; however, based on GEMCAD preclinical studies and recent publications, no other biomarker of interest was identified at the time of database closure.

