5.2. SECONDARY OBJECTIVES

- To analyse secondary biomarkers (MMP-7, IGF-1, IGFBP-3, amphiregulin, and epiregulin as well as other relevant biomarkers, which may arise during trial implementation) in the serum and tumour tissue, to predict acquired chemoresistance. • OS based on the proposed classification.
- Objective response rate (ORR) according to RECIST 1.1 (46). • To describe the safety profile, including AE incidence and significant changes in laboratory parameters after the bi-weekly administration of cetuximab at 500 mg/m² q2w as first-line therapy.
- To evaluate the ORR, duration of response (DoR), and OS in wt-KRAS/NRAS mCRC patients treated with bi-weekly cetuximab in combination with FOLFOX6 (m) or FOLFIRI (m) as a first-line chemotherapy regimen, according to the expression of the proposed biomarkers.

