- h. If thoracic CT scan at selection did not show any chest abnormality, chest X-ray imaging were performed in subsequent evaluations. A CT scan was performed to confirm any abnormality identified upon chest X-ray imaging performed after selection, and all subsequent evaluations were thoracic CT imaging.
- i. Response evaluation was conducted according to the revised RECIST 1.1 criteria, every 12±1 weeks until PD. Subject follow-up was performed regardless of discontinuation or a delay in treatment.
- j. ECOG PS evaluation (on day 1 of each treatment cycle).
- k. Tumour evaluation and serum CEA test was performed every 12 weeks and at the follow-up visit only in subjects who have withdrawn from the trial for reasons different from PD, and in those who have not had a serum CEA test in the previous 12 weeks.
- l. Paraffin embedded tumour block was sent to the central laboratory (Fundación Jiménez Díaz) at selection. The centralised evaluation laboratory perform a tumour block quality assessment. It was compulsory that KRAS and NRAS mutational status (wtKRAS and NRAS) was confirmed by a validated laboratory before the inclusion of any subject.
- m. Follow-up of all subjects who permanently discontinued the treatment before disease progression (e.g. due to unacceptable toxicities) was conducted to evaluate PFS (i.e., tumour imaging) every 12± 1 week until PD or until the end of study (unless the reason for study discontinuation was total consent withdrawal). After PD, all subjects underwent a follow-up assessment of disease status, subsequent cancer therapy, and survival assessment every 12 ± 1 weeks until the end of study (maximum of 24 months).
- n. Blood samples for biomarker analysis were withdrawn before the study treatment initiation and every 12 weeks ± 1 weeks until PD.

Table 3: SDV schedule

Form	Variables
Eligibility	Pathology report, staging, prior treatment.
Demographics	Date of birth, ECOG PS, ICF (signature, date, and completion)
Primary tumour	Diagnosis date, location, staging and surgery
Adjuvant or neoadjuvant treatment	Yes/No
KRAS/NRAS	Central reviewing
Baseline biochemistry and SAE biochemistry	LDH, creatinine, bilirubin, and CEA
Baseline haematology and SAE haematology	Haemoglobin, platelets, and leukocytes

Metastasis	Nº affected organs and hepatic M1 (number and size)
CT scans or MRI	All variables (date, lesions measure, location, new lesions) and RECIST criteria
AEs	Grade and need of SAE communication

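### The SAP's acquired-resistance endpoint names BRAF and PI3K, not the objective's markers, and the plan gives neither a definition of acquired resistance nor an analysis of the repeated serum values

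*SAP*

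**What the plan says.** Protocol 4.6.2 states the objective as "Secondary biological markers (MMP-7, IGF-1 and IGFBP3) will be analyzed in serum and tumor tissue to predict acquired resistance". SAP 5.2 restates it with a longer, open-ended list: "To analyse secondary biomarkers (MMP-7, IGF-1, IGFBP-3, amphiregulin, and epiregulin as well as other relevant biomarkers, which may arise during trial implementation". SAP 4.2 then closes that list, reporting that "no other biomarker of interest was identified at the time of database closure".

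The endpoint that should implement this objective is the first bullet of SAP 6.5.1.2: "Serum and tumor tissue secondary biomarkers evaluated to predict acquired chemo-resistance including BRAF and PI3K".

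Elsewhere BRAF and PI3K have a different role. The protocol synopsis gives the primary objective as "Validation of the biomarkers BRAF, IGF1P / MMP7 (DP) and PI3K-PTEN to predict PFS", and SAP 5.1 and 6.5.1.1 use them in the same way. The SAP describes their determination as "BRAF and PI3K mutations by RT-qPCR, and PTEN expression by immunohistochemistry".

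On sampling, the schedule in SAP section 6 (Table 2) places the tumour block at selection only. For serum, a footnote to that table says "Blood samples for biomarker analysis were withdrawn before the study treatment initiation and every 12" weeks, with a one-week window, until progression. Protocol 5.1 agrees: biomarkers are measured before enrolment and only blood is repeated.

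**The concern.** The two markers named in the endpoint are not the markers named in the objective. An analyst working from SAP 6.5.1.2 and 6.5.1.5 would find BRAF and PI3K named, a ready-made PFS model for each, and nothing else to run. The likely product is a second look at baseline mutations under the label of acquired resistance.

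The stated rationale points elsewhere. Protocol 4.4.2 reports that MMP-7 rises as disease progresses and that this accompanies a fall in IGFBP-3. That hypothesis concerns change over time, and it is the evident reason for repeating the blood draws. If no analysis uses those draws, patients give serial samples for an objective that is never addressed.

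**Working it through.** No figure in the plan bears on this point and no arithmetic is needed. The check sets the sections side by side.

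1. **Markers in the objective.** Protocol 4.6.2: MMP-7, IGF-1, IGFBP-3. SAP 5.2: the same three plus amphiregulin and epiregulin, so five named markers.
2. **Markers in the endpoint.** SAP 6.5.1.2: BRAF and PI3K. Overlap with the five in step 1: none.
3. **Could the open list explain the difference?** No. SAP 4.2 says nothing was added by database closure. BRAF and PI3K were in any case already primary-objective markers, so they were not newly arising candidates.
4. **Can BRAF and PI3K vary under treatment in these data?** No. The block is scheduled at selection, and the documents describe no repeat biopsy, no block at progression and no blood-based mutation test. Each patient has one baseline reading.
5. **Which data could show change?** The serum samples: baseline, then every 12 weeks (±1) until progression.
6. **Does any analysis use them?** SAP 6.5.1.5 lists the clinical endpoints as ORR, DoR, PFS and OS. Its multivariable model takes LDH and CEA from blood, as adjustment variables. The four scores use clinical factors alone or with BRAF, PI3K/PTEN or DP. MMP-7 enters only as the tissue component of DP. None of the five markers enters as a repeated serum value.
7. **Is there a table for them?** The shells in SAP section 7 cover disposition, protocol deviations, baseline characteristics by BRAF, PI3K/PTEN and DP, treatment compliance, exclusions, response by BRAF, PFS, OS and toxicity. None is for serum markers.
8. **Is the outcome defined?** Neither document says what counts as acquired resistance. Protocol 10.2.2 and the evaluation criteria in the SAP synopsis list only ORR, duration of response, OS and safety as secondary endpoints. The resistance item appears in the protocol synopsis and in SAP 6.5.1.2 without a statistical definition. The gap therefore began in the protocol.

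Steps 1 to 4 establish the marker mismatch. Steps 5 to 8 establish the larger problem: correcting the names alone would still leave no outcome and no method.

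**The case against.** Four objections deserve an answer.

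**Serum was not dropped.** The endpoint opens with serum and tumour tissue markers, and *including* is not an exclusive word. This stands. A reader might infer that the SAP replaced the serum markers with BRAF and PI3K, but the text does not say so and SAP 5.2 still lists them. What remains is that the endpoint leaves them unnamed and the SAP gives them no method.

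**The aim is to predict, and a baseline marker can predict.** This also stands. It is tempting to say that the endpoint cannot show acquired resistance at all. The documents support only the narrower statement that BRAF and PI3K cannot show change under treatment. They could be studied as baseline predictors of later resistance, but that needs a defined outcome, and there is none.

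**Duration of response already separates late from early progression.** It does so for responders, since it runs from first response to progression. It leaves out patients whose best result is stable disease, and the plan links neither it nor any serum model to the resistance endpoint.

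**The outcome may simply be PFS.** A reader might infer this and then count the patients expected to progress before the first scan as wrongly classed with acquired resistance. The documents do not support such a count. No outcome is stated for this endpoint, PFS events include deaths, and the PFS clock starts at signature of consent, so it need not align with the week-12 scan. The fault is a missing definition, and no patient number is attached to it here.

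**Conclusion.** The point holds in this form: the endpoint names only primary-objective markers, those markers are single baseline readings, acquired resistance is undefined, and nothing in the analysis section or table shells uses the repeated serum values. This is more than missing detail, because the only markers named are the wrong ones for the objective.

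Its size is one secondary objective left without an analysis. No primary result, sample size, error rate or safety summary changes. It should be corrected, but it does not threaten the trial's main conclusion.

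The verdict assumes that the schedule in SAP section 6 describes what was collected, and that no separate laboratory analysis plan exists outside these documents. If such a plan exists, the SAP should refer to it; the mismatch in 6.5.1.2 would still need correcting.

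**What to change.** - **Markers.** In SAP 6.5.1.2 replace the reference to BRAF and PI3K with the list in SAP 5.2, saying for each marker whether it is measured in serum, tissue or both. Keep BRAF and PI3K under the primary objective, or label them as fixed baseline covariates.
- **Outcome.** Define it for analysis as RECIST progression after documented disease control (CR, PR or SD) at the first scheduled post-baseline assessment. Use each patient's actual assessment date, so that the ±1-week window does not misclassify anyone.
- **Model.** Run a landmark analysis from that assessment. Fit a Cox model for each serum marker, entered as the last value drawn before the progression scan and not at it, adjusted for the baseline value. The lag matters because blood is drawn alongside imaging, so a concurrent value may only reflect tumour burden.
- **Other rules.** State how death without progression is handled, for example as a censoring event in a cause-specific analysis or as part of the outcome. Report patients who progress at or before the first assessment separately.
- **Status.** Label the analysis post hoc. The SAP synopsis already gives AUC results for the clinical and biomarker scores, so a definition written now cannot be presented as prespecified.

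A joint model would be a reasonable alternative; what matters is that one method is stated. The cost is SAP wording and one analysis of samples already scheduled, with no new sampling. The downsides are that early progressors are left out of this secondary analysis and that serum values may be up to about 12 weeks old when used.
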